### **10.4. Radiotherapy**

Patients will have received standard total of 60Gy in 2 Gy daily fractions 5 days a week for 6 weeks

## **11. SAFETY ASSESSMENT**

### **11.1. Adverse Event (AE) and AE Reporting**

#### **11.1.1. Definition of a Clinical Adverse Events**

Per the International Conference of Harmonization (ICH) an AE is any unfavorable and unintended medical occurrence/sign (including an abnormal laboratory finding), symptom or disease in a patient or clinical investigation subject administered a pharmaceutical product and which does not necessarily have a causal relationship with this treatment.

An AE can therefore be any unfavorable and unintended sign, symptom, or disease temporally associated with the use of a medicinal product, whether or not considered related to the medicinal product. Pre-existing conditions which worsen during a study are also to be reported as AEs.

Each AE term is mapped to a MedDRA preferred term.

#### 11.1.2. Reporting and Grading of an Adverse Event

Adverse events will be reported and graded following National Cancer Institute Common Terminology Criteria for Adverse Events version 5.0 (CTCAE). Accordingly, intensity of all adverse events will be graded on a five-point scale (Grade 1 to 5) and reported in detail on the CRF. Reporting of AE based on CTCAE terms and corresponding grading are an integral part of safety/AE/SAE reporting in this study and will have to be strictly followed. Adverse events not listed on the CTCAE should be graded as instructed in table 3.

#### 11.1.3. Causal Relationship between 'Treatment' and the Adverse Event

The causality relationship of study 'treatment' to the adverse event will be assessed by the investigator as either: **Yes or No or probably**

If there is a reasonable suspected causal relationship to the study treatment, i.e. there are facts (evidence) or arguments to suggest a causal relationship, drug-event relationship should be assessed as **Yes**.

The investigator should provide his/her assessment as to whether an AE is related to each individual component of the study treatment regimen (i.e. temozolomide and/or avelumab).

The following criteria should be considered in order to assess the relationship as **Yes**:

- Reasonable temporal association with drug administration
- It may or may not have been produced by the subject's clinical state, environmental or toxic factors, or other modes of therapy administered to the subject.
- Known response pattern to suspected drug
- Disappears or decreases on cessation or reduction in dose
- Reappears on rechallenge.

The following criteria should be considered in order to assess the relationship as **No**:

- It does not follow a reasonable temporal sequence from administration of the drug.
- It may readily have been produced by the subject's clinical state, environmental or toxic factors, or other modes of therapy administered to the subject.
- It does not follow a known pattern of response to the suspected drug.
- It does not reappear or worsen when the drug is re-administered.

### 11.2. Serious Adverse Event

A serious adverse event is any adverse event that fulfils at least one of the following criteria:

- is fatal; (results in death; NOTE: death is an outcome, not an event)

- is Life-Threatening (NOTE: the term "Life-Threatening" refers to an event in which the subject was at immediate risk of death at the time of the event; it does not refer to an event which could hypothetically have caused a death had it been more severe).
- requires in-patient hospitalization or prolongation of existing hospitalization;
- results in persistent or significant disability/incapacity;
- is a congenital anomaly/birth defect;
- is medically significant or requires intervention to prevent one or other of the outcomes listed above

All AEs that do not meet any of the criteria for seriousness should be regarded as **nonserious AEs**.

The terms "severe" and "serious" are not synonymous. Severity (or intensity) refers to the grade of a specific AE, e.g., mild (Grade 1), moderate (Grade 2), or severe (Grade 3) myocardial infarction. "Serious" is a regulatory definition (see previous definition) and is based on subject or event outcome or action criteria usually associated with events that pose a threat to a subject's life or functioning. Seriousness (not severity) serves as the guide for defining regulatory reporting obligations from the Sponsor to applicable regulatory authorities. Severity and seriousness should be independently assessed when recording AEs and SAEs on the CRF.

The study will comply with all local regulatory requirements and adhere to the full requirements of the **ICH Guideline for Clinical Safety Data Management, Definitions and Standards for Expedited Reporting**

### **11.3. Adverse Events of Special Interest**

Adverse events of special interest will include those of autoimmune origin (iAE).

Since inhibition of PD-L1 stimulates the immune system, immune-related AEs (irAEs) may occur.

### **11.4. Treatment Emergent Adverse Event (TEAE) Requiring Avelumab Discontinuation or Modifications**

The following TEAE's require permanent treatment discontinuation of avelumab:

- **Any Grade 4 TEAE require treatment discontinuation with avelumab** except for single laboratory values out of normal range that are unlikely related to study treatment as assessed by the Investigator, do not have any clinical correlate, and resolve within 7 days with adequate medical management
- **Any Grade 3 TEAE's require treatment discontinuation with avelumab except for any of the following:**
  - Transient ( $\leq$  6 hours) Grade 3 flu-like symptoms or fever, which is controlled with medical management
  - Transient ( $\leq$  24 hours) Grade 3 fatigue, local reactions, headache, nausea, emesis that resolves to Grade  $\leq$  1

- Single laboratory values out of normal range (excluding Grade  $\geq 3$  AST or ALT combined with  $\geq 2$  ULN total bilirubin) that are unlikely related to study treatment according to the Investigator, do not have any clinical correlate, and resolve to Grade  $\leq 1$  within 7 days with adequate medical management
- Change in ECOG PS to  $\geq 3$  that does not resolve to  $\leq 2$  within 14 days (infusions should not be given on the following cycle, if the ECOG PS is  $\geq 3$  on the day of Avelumab administration)

- **Any Grade 2 TEAE should be managed as follows:**

If a Grade 2 ADR resolves to Grade  $\leq 1$  by the last day of the current cycle, treatment may continue.

- If a Grade 2 TEAE does not resolve to Grade  $\leq 1$  by the last day of the current cycle, infusions should not be given on the following cycle. If at the end of the following cycle the event has not resolved to Grade 1, the subject should permanently discontinue treatment with avelumab. TEAE (except for hormone insufficiencies, that can be managed by replacement therapy; for these hormone insufficiencies, up to 2 subsequent doses may be omitted).
- Upon the second occurrence of the same Grade 2 TEAE (except for hormone insufficiencies that can be managed by replacement therapy) in the same subject, treatment with avelumab has to be permanently discontinued.
- Infusion-related reactions, hypersensitivity reactions (Grades 1 to 4), and tumor lysis syndrome should be handled according to guidelines provided.

The Management for Symptoms of Infusion-Related Reactions are listed in the table below:

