##### **Exploratory objectives:**

To explore biomarkers that could predict treatment response to avelumab such as: the tumor immunoscore, presence and extent of PD-L1 expression on tumor cells and microglia/macrophages within the tumor

To correlate the OS and PFS in relation to the baseline value and the change from baseline to week 52 visit and every 52 weeks /or end of study visit (depending on whether the latter occurs before or after week 260) neurocognitive function as measured by the evoked potential P300 (normal), the baseline corticosteroid dose, the total cumulative corticosteroid dose over the whole study duration, the total cumulative temozolomide dose per BSA since diagnosis and the presence and severity of immune related adverse events (irAE's).

To assess and compare above mentioned biomarkers in tissue samples from patients with second surgical resection ie treatment failures.

To assess in this GBM population the duration of pseudoprogression and the lagtime needed for immunotherapy to become effective.

**Study Design:** This is a single center, phase 2, open-ended, open label, add-on, single dose study in patients receiving standard therapy for newly diagnosed GBM with

a projected duration of 5 years (260 weeks). In total 30 patients who meet the entry criteria will be entered into the study within 3 weeks of finishing their last day of combined radiotherapy/temozolamide. Avelumab will be initiated concurrently with the initiation of the first 5 days, monthly cycle of temozolamide and continued until the occurrence of a termination event defined as one of the following: 1) clinical evidence of neurological deterioration resulting in an ECOG score of at least 3 or more, unexplained by other comorbidities, unchanged by an increase in corticosteroid dose and sustained for at least two weeks or 2) treatment emergent adverse event (TEAE) of grade 3 or more or 3) withdrawal of patient consent.

A local pathology report will constitute adequate documentation of histology for study inclusion.

The tumor block used for diagnosis of GBM must be collected for each patient and sent for MGMT assessment (if not already done), biomarker and immunoscore analysis. The availability of these samples is mandatory for the baseline visit.

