### **4.2. Treatment Phases of the Study**

**Combination Phase:** Upon completion of the standard combination therapy of radiotherapy (total dose 60 Gy, administered as daily 2Gy fractions, 5 days/week or as per local standard) and temozolomide (75 mg/m^2/day p.o. qd) and a treatment break of no more than 21 days, the combination phase will start. Patients will receive temozolomide and avelumab for 6 cycles of 28 days each. During the 1st cycle Temozolomide will be given the first 5 days at a dose of 150mg/m^2/day p.o. In the next cycle, the temozolomide dose should be escalated to 200/mg/m^2 if permitted by the patient's hematological and non-hematological toxicity profile (as per NCI-CTC AE version 5). The temozolomide dose will be adjusted according to hematological and non-hematological toxicity as per temozolomide's product monograph (appendix 4). Avelumab will be administered on day 1 and day 15 of each cycle at a dose of 10mg/kg IV. Avelumab therapy will be withheld according to the occurrence and severity of avelumab emergent adverse events as per table 3. Patients will continue the

combination of temozolomide (150 – 200mg/m^2 per day PO X5 days Q28days) and avelumab (at 10mg/kg dose, IV on days 1 and 15 per cycle) until 6 cycles are completed or until the occurrence of a termination event.

**Monotherapy Phase:** Upon completion of the Combination Phase or upon stopping temozolomide because of temozolomide related toxicity/tolerability issues or patient choice, the patient will continue into the avelumab Monotherapy Phase. Avelumab 10mg/kg IV Q2weeks will be continued as monotherapy until the occurrence of a termination event defined as one of the following: 1) clinical evidence of neurological deterioration resulting in an ECOG score of at least 3 or more, unexplained by other comorbidities, unchanged by an increase in corticosteroid dose and sustained for at least two weeks or 2) treatment emergent adverse event (TEAE) of grade 3 or more or 3) withdrawal of patient consent.

Patients who experience irAE's may according to table 3 directives have their avelumab therapy suspended.

The use of Bevacizumab or re-irradiation will not be allowed in the study and will be considered as evidence of a termination event.

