### **9.3.4. Assessments at end of study**

An end of treatment study visit will occur when:

- 1) Grade 3 or higher avelumab related toxicity occurs
- 2) Evidence as per the iRANO criteria of tumor progression occurs and patient does not wish to continue treatment
- 3) Patient wishes for any reason to discontinue treatment or withdraw from the study. Clinical evidence of neurological deterioration resulting in an ECOG score

of at least 3 or more, unexplained by other comorbidities, unchanged by an increase in corticosteroid dose and sustained for at least two weeks.

A history, physical and neurological exam will be performed by a physician. Laboratory test as per schedule will be drawn. If any of the latter have already been performed to confirm the AE or tumor progression on the basis clinical neurological deterioration, then they need not be repeated.

A study specified gadolinium enhanced MRI or CT scan will be performed within 2 weeks of the end of study visit for all patients after 52 weeks.

Patients however who discontinue the study treatment on the basis of avelumab treatment related AE's or clinical evidence of tumor progression a study specified MRI or CT scan will be done at the discretion of the investigator.

Patients who prematurely discontinue study treatment will be encouraged to continue into the Extended Safety Follow-up phase of the study

Patients who not only end treatment but also withdraw from the study, for any reason, will be encouraged to have telephone follow ups every month in order to obtain survival information with regards to OS. Pathology samples will be obtained for repeat biomarker analysis if a second tumor surgery occurs

**NOTE:** Since the actual duration of pseudoprogression and the time for immunotherapies to become effective in patients with GBM are still unknowns patients will be allowed at the investigator and patient discretion to continue on study treatment after confirmation of radiographic progression unless there is significant drug toxicity Grade 3 or higher AE's unrelated to avelumab such as those secondary to intercurrent illness or temozolomide therapy do not constitute for the purpose of this study a reason to withhold avelumab therapy or withdraw the patient from the study.

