## **10. INVESTIGATIONAL MEDICINAL PRODUCT**

### **10.1. Dose and Schedule of Test Drug**

Avelumab is a fully human IgG1 antibody directed against PD-L1. Avelumab binds PD-L1 and blocks the interaction between PD-L1 and its receptors PD-1 and B7.1. This removes the suppressive effects of PD-L1 on anti-tumor CD8+ T cells, resulting in the restoration of cytotoxic T cell response.

Avelumab will be administered intravenously every 14 days starting the same day as the first day of the first 5 days po temozolomide treatment. Temozolomide's 28 days cycle will be repeated 6 times or until grade 3 or higher temozolomide related treatment AE's. Avelumab will be continued IV q14 days for 260 weeks or until grade 3 or higher avelumab treatment-related AE's occurs and independent of whether the patient continues or completes the 6 cycles of temozolomide.

Avelumab may be withheld temporarily in the case of irAE according to the irAE's algorythms (table 3)

Temozolomide dose may be adjusted or withheld according to the directives in the temozolomide's product monograph (appendix 4)

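### Protocol 11.4, the synopsis and 4.2 stop avelumab for Grade 3 or higher events whatever their cause, while 9.3.4 and 10.1 stop it only for avelumab-related ones

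*Protocol*

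**What the plan says.** **Places that stop avelumab regardless of cause.** Protocol 11.4 requires permanent discontinuation for any Grade 4 TEAE. Its one exemption is for single laboratory values judged unlikely to be related that "do not have any clinical correlate, and resolve within 7 days with adequate medical management". It requires the same for any Grade 3 TEAE outside a list of exceptions: brief flu-like symptoms or fever, brief fatigue, headache, nausea or similar, certain laboratory values, and an ECOG item. The laboratory exception at Grade 3 begins "Single laboratory values out of normal range (excluding Grade" and carves out raised AST or ALT combined with raised bilirubin. The synopsis (Study Design) and 4.2 continue avelumab "until the occurrence of a termination event defined as one of the following", and one of the listed events is a "treatment emergent adverse event (TEAE) of grade 3 or more", with no exceptions.

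**Places that stop it only for avelumab-related events.** Protocol 10.1 sets a limit of 260 weeks and otherwise continues avelumab "until grade 3 or higher avelumab treatment-related AE's occurs and independent of whether the patient continues or completes the 6 cycles of temozolomide". Protocol 9.3.4 calls the end-of-treatment visit when "Grade 3 or higher avelumab related toxicity occurs". Its closing note takes up "Grade 3 or higher AE's unrelated to avelumab such as those secondary to intercurrent illness or temozolomide therapy" and says that events of this kind justify neither holding back a dose nor removing the patient.

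**A place that does not say.** Protocol 6.2 lists toxicity of Grade 3 or higher among the reasons for which the investigator can or must stop treatment, and names no drug.

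**The concern.** During the Combination Phase every patient takes two drugs, and temozolomide has its own toxicity. A severe event caused by temozolomide or by an intercurrent illness is a foreseeable situation, and 9.3.4 anticipates it by name. The protocol gives the investigator two opposite instructions for that situation: end avelumab permanently, or do not miss a dose. Either action departs from one section.

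What is at stake is the patient's treatment. Under 11.4 a patient can lose the study drug for good because of an event that another section says must not affect its dosing. A monitor or safety board checking the decision has no single rule to check it against.

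**Working it through.** No arithmetic applies; the check is a comparison of the current text.

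**1. The rules side by side**

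| Place in Protocol | Event that ends avelumab | Must it be avelumab-related? |
|---|---|---|
| 11.4, Grade 4 | Any TEAE, one laboratory exemption | No |
| 11.4, Grade 3 | Any TEAE outside the listed exceptions | No |
| Synopsis and 4.2 | Any TEAE of Grade 3 or more | No |
| 10.1 | Grade 3 or higher | Yes |
| 9.3.4 | Grade 3 or higher | Yes; unrelated events expressly excluded |
| 6.2 | Toxicity of Grade 3 or higher, can or must | Drug not named |

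I found no clause saying which section prevails.

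**2. Could TEAE already mean avelumab-related?** If it did, the conflict would vanish. But 11.4 exempts certain laboratory TEAEs because they are unlikely to be related, which makes sense only if a TEAE can be unrelated. Section 2 also adds treatment-related as a separate qualifier to TEAE.

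**3. A case that does not turn on laboratory wording.** Take Grade 3 fatigue, judged to be caused by temozolomide and not by avelumab, lasting more than 24 hours.
- 11.4: the fatigue exception covers 24 hours at most, so avelumab stops permanently.
- Synopsis and 4.2: a termination event.
- 10.1: not an avelumab treatment-related event, so avelumab continues.
- 9.3.4: unrelated and due to temozolomide, so avelumab is not even withheld.

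What happens to temozolomide is a separate matter (Appendix 4, Table 9).

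**4. The laboratory exemptions in 11.4**

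| Condition | Grade 3 | Grade 4 |
|---|---|---|
| Single value | Yes | Yes |
| Unlikely related to study treatment | Yes | Yes |
| No clinical correlate | Yes | Yes |
| 7-day limit | Yes | Yes |
| Excludes Grade ≥3 AST/ALT with bilirubin ≥2 × ULN | Yes | Not stated |
| Recovery target | Grade ≤1 | Only 'resolve' |

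Two points follow. First, 'study treatment' is ambiguous: 11.1.3 counts both temozolomide and avelumab in the regimen, while 9.3.4 appears to use the term for avelumab. A temozolomide-caused Grade 4 laboratory value fails the exemption on the first meaning and may pass on the second. Second, the liver exclusion is printed only at the lower grade.

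**5. Frequency.** The only overall Grade ≥3 adverse-event rate for avelumab at 10 mg/kg is for treatment-related TEAEs in another trial (Section 2: 124/1300 = 9.5%). It says nothing about unrelated events, so no expected count is given here.

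**The case against.** The best case against is that the intent is recoverable. Section 9.3.4 addresses this exact situation, 10.1 agrees with it, and the SAP (1.3.1) and Protocol 12.3.1 define the primary endpoint by avelumab-related events. On that view 11.4, the synopsis and 4.2 are lagging text. The protocol is also loose with its terms: 5.1 attaches treatment-emergent to avelumab where 12.3.1 says avelumab related, and the Grade 2 rule in 11.4 mixes ADR with TEAE. The trial has one center, so divergence between sites is not an issue.

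Most of this stands, and it decides the direction of the fix. It does not remove the conflict. Section 11.4 is the section dedicated to discontinuation, the 9.3.4 sentence sits in a note on end-of-study assessments, and the laboratory exemption defeats the reading of TEAE as related.

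A reader might infer three stronger things that the documents do not support.
- **That the primary endpoint rate is distorted.** The SAP counts avelumab-related events, so a stop for an unrelated event does not enter that count by definition.
- **That a predictable number of patients will be affected.** That needs a rate of unrelated Grade 3 or higher events, which the documents do not give. Events covered by the 11.4 exceptions would also have to be removed.
- **That the Grade 4 exemption leaves patients with serious liver injury on avelumab.** It covers only single values judged unlikely to be related, and AST or ALT combined with bilirubin is naturally two values. If the event is handled as a hepatic irAE, Table 3 permanently stops avelumab at Grade 3 to 4. Unqualified 'resolve' may even mean full resolution, which is stricter than Grade 1.

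**Conclusion.** The contradiction is in the current text and should be corrected. For a Grade 3 or higher event that is unrelated to avelumab and outside the 11.4 exceptions, 11.4, the synopsis and 4.2 end avelumab permanently, while 9.3.4 and 10.1 leave it running. The consequence is large for the patient concerned. How many patients that will be cannot be derived from the documents.

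The conclusion assumes that TEAE carries its ordinary meaning, which 11.4's own exemption requires, and that no section takes precedence, since none is said to. The missing liver exclusion at Grade 4 is a minor drafting gap, rare in practice and partly covered elsewhere.

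**What to change.** Align 11.4, the synopsis and 4.2 with 9.3.4 and 10.1. Suggested rule: avelumab is permanently discontinued for a Grade 3 or higher event outside the 11.4 exceptions unless the event is assessed as unrelated to avelumab. With it:

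- count the 'probably' category of 11.1.3 as related;
- leave irAEs to Table 3, which in several rows allows avelumab to resume after a first Grade 3 event;
- leave temozolomide toxicity to Appendix 4;
- name avelumab in the toxicity line of 6.2;
- replace 'study treatment' in both laboratory exemptions with the drug meant.

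Minor addition: repeat in the Grade 4 laboratory exemption the exclusion of Grade ≥3 AST or ALT combined with total bilirubin ≥2 × ULN. Do not add a Grade ≤1 target there, because it could loosen the present wording.

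The cost is a few lines of protocol text, with no change to sample size or analysis. The real downside is attribution: while both drugs are given, some avelumab-related events could be assigned to temozolomide and avelumab continued. Counting 'probably' as related limits this. Rarely, a patient with the combined Grade 4 liver pattern would stop avelumab who might otherwise have continued.

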Paraffin embedded blocks containing formalin-fixed tumor tissue representative of the glioblastoma diagnosis is the preferred sample (if available, and of sufficient quality), otherwise, a partial tumor block, or pathology material should be sent. If surgery was not performed but biopsy was performed (or if it is not possible to send FFPE tumor tissue blocks) at least 10 unstained, uncovered slides must be sent.

The study will consist of 3 different phases: a Combination Phase, a Monotherapy Phase and an Extended Safety Follow-up Phase

**Combination Phase:** Upon completion of the standard combination therapy of radiotherapy (total dose 60 Gy, administered as daily 2Gy fractions, 5 days/week or as per local protocol) and temozolamide (75 mg/m^2/day p.o. qd) and a treatment break of no more than 21 days, the combination phase will start. Patients will receive temozolamide and avelumab for 6 cycles of 28 days each. During the 1st cycle Temozolamide will be given the first 5 days at a dose of 150mg/m^2/day p.o. In the next cycle, the temozolamide dose should be escalated to 200/mg/m^2 if permitted by the patient's hematological and non-hematological toxicity profile (as per NCI-CTC AE version 5). The temozolamide dose will be adjusted according to hematological and non-hematological toxicity as per temozolamide's product monograph (appendix 4). Avelumab will be administered on day 1 and day 15 of each cycle at a dose of 10mg/kg IV. Avelumab therapy will be withheld according to the occurrence and severity of avelumab emergent adverse events as per table 3. Patients will continue the combination of temozolamide (150-200mg/m^2 per day PO X5 days Q28days) and avelumab (at 10mg/kg dose, IV on days 1 and 15 per cycle) until 6 cycles are completed or until the occurrence of a termination event.

**Monotherapy Phase:** Upon completion of the Combination Phase or upon stopping temozolamide because of temozolamide related toxicity/tolerability issues or patient choice, the patient will continue into the avelumab Monotherapy Phase. Avelumab 10mg/kg IV Q2weeks will be continued as monotherapy until the occurrence of a termination event.

Patients who experience irAE's may according to table 3 directives have their avelumab therapy suspended.

The use of Bevacizumab or re-irradiation will not be allowed in the study and will be considered as evidence of disease progression.

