### **6.2. Criteria for Premature Withdrawal**

#### **Withdrawal from the study treatment /study**

The investigator can/must discontinue study treatment for a patient in the event of:

- Progressive disease (as per iRANO)
- Intercurrent illness
- Unacceptable toxicity (grade 3 or higher)
- Protocol violation
- Pregnancy
- Patient request
- In the case that the patient decides to prematurely discontinue study treatment he/she will be offered to continue into the Extended Safety Follow-up Phase
- In the case the patient decides not to or is unable to continue into the extended follow up phase then he/she will be withdrawn from the study. He /she will with the patient's permission be followed for survival assessment with monthly

telephone calls. Otherwise the patient will be considered lost to follow-up. The outcome of these discussions should be documented in both the medical records and in the CRF.

- Similarly, the investigator has the right to withdraw patients from the study in the event of intercurrent illness, unacceptable toxicity, protocol violation, pregnancy and administrative or other reasons. Patients have the right to withdraw from the study at any time for any reason.
- An excessive rate of withdrawals can render the study uninterpretable; therefore, unnecessary withdrawal of patients should be avoided.

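### Protocol sections give opposite instructions on stopping avelumab after grade 3 or higher events unrelated to it, and section 11.4 has no carve-out for the Table 3 immune-related rules

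*Protocol*

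**What the plan says.** **Stops that do not depend on cause.** The synopsis (Study Design) lists among the termination events "treatment emergent adverse event (TEAE) of grade 3 or more or 3) withdrawal of patient consent". Section 4.2 repeats it: "treatment emergent adverse event (TEAE) of grade 3 or more". Section 11.4, on permanent discontinuation, states "Any Grade 3 TEAE's require treatment discontinuation with avelumab except for any of the following". Its exceptions are brief flu-like symptoms or fever, a short list of other transient symptoms, isolated laboratory values that resolve within 7 days and are unlikely to be related to study treatment, and an ECOG item. Its grade 4 rule has only a laboratory exception. Section 6.2 lists toxicity of grade 3 or higher without naming a drug.

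**Stops for avelumab-related events only.** Item 1 of section 9.3.4 ends treatment when "Grade 3 or higher avelumab related toxicity occurs". The note in the same section says that grade 3 or higher events unrelated to avelumab, including those from temozolomide or intercurrent illness, "do not constitute for the purpose of this study a reason to withhold avelumab therapy or withdraw the patient from the study". Section 10.1 likewise continues avelumab until a grade 3 or higher avelumab-related event, whatever happens with temozolomide. Section 4.2 also says that "upon stopping temozolomide because of temozolomide related toxicity/tolerability issues or patient choice, the patient will continue into the avelumab Monotherapy Phase".

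**Immune-related events.** The synopsis says "Patients who experience irAE's may according to table 3 directives have their avelumab therapy suspended". Both the synopsis and 4.2 also state, in mandatory terms, that avelumab is withheld as Table 3 directs. Sections 10.1 and 11.6 point to Table 3 as well. Section 11.4 refers infusion reactions, hypersensitivity and tumor lysis syndrome to other guidance but does not name irAEs.

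**Primary endpoint.** SAP 1.3.1 and Protocol 12.3.1 count avelumab-related events leading to permanent or transient discontinuation. Protocol 5.1 speaks of avelumab treatment-emergent events instead.

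**The concern.** The primary endpoint is built on discontinuations of avelumab, so the rule that triggers a discontinuation is part of how the endpoint is measured. If two sections give opposite instructions for the same event, the recorded outcome depends on which section the investigator follows. Whichever is followed, another written rule is breached, and 6.2 makes a protocol violation itself a ground for discontinuation. Avelumab exposure, which lies behind the survival and response results, also depends on the choice.

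**Working it through.** No figure in the plan is at issue. The check sets the rules side by side and applies them to concrete cases.

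**1. Does treatment-emergent already mean avelumab-related?** No. Section 2 uses treatment-related as a separate qualifier of treatment-emergent events. The laboratory exception in 11.4 turns on relatedness, which would be largely redundant if only related events counted.

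**2. Cases**

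| Event | Synopsis, 4.2 | 11.4 | 9.3.4, 10.1 | Table 3 |
|---|---|---|---|---|
| Temozolomide-related grade 3 cytopenia lasting over 7 days | Stop | Permanent stop | Continue, no hold | Not applicable |
| First grade 3 immune-related rash | Stop, but Table 3 also cited | Permanent stop | Stop; 10.1 also permits a Table 3 hold | Hold, then resume |
| Grade 4 endocrinopathy that improves to grade 1 | Stop, but Table 3 also cited | Permanent stop | Stop; 10.1 also permits a Table 3 hold | Hold, then resume |

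The cytopenia fails the 11.4 laboratory exception on its 7-day limit. A shorter one is unclear: the exception requires a value unlikely to be related to study treatment, and 11.1.3 counts temozolomide as a component of study treatment. The hormone-insufficiency exception in 11.4 applies at grade 2 only, so it does not cover the third case.

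**3. Section 4.2 against itself.** Section 10.1 gives a grade 3 or higher temozolomide-related event as an end to temozolomide. Under 4.2, a patient stopped for that reason moves to avelumab monotherapy, yet the same event is a termination event.

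**4. Count over Table 3.** There are nine irAE types, taking hypophysitis apart from other endocrine events. Severe and life-threatening are read as grades 3 and 4, in line with 11.11.2.

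- First grade 3, hold then resume against a permanent stop in 11.4: colitis/diarrhea, rash, renal, endocrine, hypophysitis, other = 6. Permanent stop in both: pneumonitis, hepatic, confirmed immune-related myocarditis (ungraded) = 3. 6 + 3 = 9.
- Grade 4, hold then resume against a permanent stop: endocrine, hypophysitis = 2. Permanent stop in both: 7. 2 + 7 = 9.

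The agreement holds at grades 3 and 4 only. At grade 2, Table 3 withholds for colitis or liver test elevation, while 11.4 lets treatment continue if the event resolves by the end of the cycle. A grade 2 liver elevation persisting beyond 5 to 7 days is managed as grade 3 to 4, hence a permanent stop, where 11.4 would allow a one-cycle hold. Suspected myocarditis is held, and avelumab restarts if symptoms improve and an immune cause is ruled out.

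**5. Effect on the primary count.** Permanent and transient discontinuations are both counted, so most of these conflicts move a patient between categories rather than in or out. The pooled count can still move in at least three ways:

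- related transient grade 3 events that 11.4 exempts but 4.2, 9.3.4 and 10.1 do not;
- an early stop for a temozolomide event, which removes the chance of a later avelumab-related discontinuation;
- grade 2 holds that Table 3 requires and 11.4 does not.

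**The case against.** The strongest reply is that the protocol can be read sensibly. The note in 9.3.4 is explicit, is worded for the study as a whole, and is the one place that directly addresses temozolomide events. For irAEs, the synopsis and 4.2 say avelumab will be withheld as per Table 3, and a specific table normally prevails over a general rule. Section 6.2 leaves discretion. Appendix 4 reduces the temozolomide dose at a grade 3 non-hematological toxicity, and temozolomide may be stopped for lesser toxicity or by choice, so the clash inside 4.2 does not arise in every case. With a single center, sites cannot diverge.

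Much of this stands. A reader might infer that irAEs have no governing rule; the documents do not support that, and the irAE part is mainly a missing carve-out in 11.4 and in the grade 3 stops of 4.2, 9.3.4 and 10.1. A reader might also infer that every temozolomide-related grade 3 event ends avelumab. That is too strong for 11.4, which exempts brief nausea, vomiting, fatigue and headache.

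The reply does not remove the conflict. No section states precedence, and 11.4, the section devoted to discontinuation, refers neither to the note nor to Table 3.

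**Conclusion.** The stopping rules contradict each other as written, and this should be fixed. The text conflict covers non-exempt grade 3 or higher events unrelated to avelumab and, for irAEs, six of nine Table 3 types at first grade 3 and two of nine at grade 4. These counts describe how far the wording conflicts; they do not measure how many patients are affected.

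A reader might multiply the section 2 rates by the sample size: 30 × 0.095 = 2.85 patients with grade 3 or higher treatment-related events, or 30 × 0.022 = 0.66 with potential irAEs of that grade. The documents do not support using these as the size. The rates come from a phase I avelumab trial, say nothing about temozolomide-related events, and include event types on which the rules agree. No rate for avelumab with temozolomide is given.

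A reader might also infer that the primary analysis is undermined. It is descriptive with no threshold, so no planned inference changes. What changes is patient dosing, avelumab exposure and the permanent/transient split. This rests on reading treatment-emergent as independent of cause, and on the absence of any precedence statement in either document.

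**What to change.** In one amendment:

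1. In the synopsis, 4.2, 6.2 and 11.4, state that grade 3 events unrelated to avelumab follow the note in 9.3.4. The clinical team should confirm the rule for unrelated grade 4 events, and that an event judged *probably* related counts as related.
2. Add irAEs to the classes that 11.4 refers elsewhere. State that Table 3 governs irAEs at grades 2 to 4 over 11.4, 9.3.4, 10.1 and the termination-event definition. The clinical team should confirm resumption after a grade 4 endocrinopathy or life-threatening hypophysitis, because this is the less cautious of the two rules.
3. Reconcile 8.4, under which other immunosuppressants lead to study withdrawal, with the infliximab and mycophenolate steps in Table 3.
4. Apply the transient grade 3 exceptions of 11.4 wherever the grade 3 stop appears.
5. Align 5.1 with the avelumab-related wording of 12.3.1 and SAP 1.3.1, and report permanent and transient discontinuations separately.

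The cost is a set of cross-references and one extra table row. No new data are needed, since 11.1.3 already asks for relatedness to each drug. The *probably* category does need a rule: 11.1.3 gives criteria only for yes and no, and 11.11.1 uses only two categories.
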